## **2.4.7 Analyses of immunogenicity variables**

ADA attributes and response endpoints defined in [Section 2.1.6](#) will be summarized in the ADA population. Titers will be also described using descriptive statistics. Further analyses may be performed, such as time to onset and duration of ADA.

The impact of positive immune response on efficacy, PK and safety endpoints may be further explored by graphical methods or descriptively, depending on ADA prevalence.

## **2.4.8 Analyses of biomarker variables**

### **2.4.8.1 Immune genetic variables**

#### *2.4.8.1.1 Descriptive analysis*

Each genetic biomarker will be summarized with descriptive statistics by treatment group and overall.

#### *2.4.8.1.2 Univariate analysis*

Each genetic biomarker will be tested for a potential prognostic/predictive effect for PFS.

A cox regression model will be conducted separately for each genetic biomarker with a treatment effect, a biomarker effect and a biomarker×treatment interaction.

For biomarkers coded as genotype (0, 1, 2), different coding may be investigated: additive, dominant or recessive.

Benjamini-Hochberg multiple correction procedure will be used to control the False Discovery Rate.

Additional analyses using ORR and OS instead of PFS might also be performed.

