## 2.1.8 Exploratory biomarker analysis

### 2.1.8.1 Immune Genetic Determinants

A blood sample will be collected at Day 1 of Cycle 1. Leukocyte DNA will be extracted and analyzed for immune genetic determinants (such as FcγR polymorphisms, HLA and KIR genotypes) and correlated with parameters of clinical response.

Germline genetic data of FcγR, HLA and KIR genes will be analyzed on blood samples collected on D1 of Cycle 1:

- FCGR polymorphisms (FCGR2A and FCGR3A): For each gene, the results will be of the form AA, Aa or aa with A and a-alleles, the major and minor allele, respectively.
- HLA genotypes: HLA-A, HLA-B and HLA-C have been typed (see [Table 5](#)).

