**Table 5 - Epitopes of HLA Class I recognized by KIR**

HLA class I	Epitope	Amino-acid at position a					Associated allotypes
		77	80	81	82	83	
HLA-B	Bw6	Ser	Asn	Leu	Arg	Gly	
	Bw4	Asn	Thr	Ala	Leu	Arg	
	Bw4	Asn	Ile	Ala	Leu	Arg	
	Bw4	Asp	Thr	Leu	Leu	Arg	
	Bw4	Ser	Thr	Leu	Leu	Arg	
	Bw4	Ser	Thr	Ala	Leu	Arg	
HLA class I	Epitope	77	80	81	82	83	
HLA-A	Aw4	Asn	Ile	Ala	Leu	Arg	A*23; A*24
	Aw4	Ser	Ile	Ala	Leu	Arg	A*32
	A3	Key residues not yet published					A*03
	A11	Key residues not yet published					A*11
HLA class I	Epitope	77	80				
HLA-C	C1	Ser	Asn				
	C2	Asn	Lys				

a Numbering from the first codon of the mature protein

- KIR genotypes: The presence or absence of 16 KIR genes will be screened. A KIR gene will be defined as present if at least one assay gives positive results; otherwise it will be defined as negative.

Results of immune genetic determinants analyses will be presented in a separate report.

In addition, samples (serum) will be collected to evaluate the potential isatuximab interference with the M protein assessment in immunoelectrophoresis and immunofixation assays. These additional samples will be collected at all time-points that M protein is analyzed for patient treated in IPd arm.

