**Table 9 - PFS subgroup analyses: covariates investigated**

Prognostic factor	Description
Age (eCRF)	<65 vs [65 - 75[ vs ≥75 years
Number of previous lines of therapy (IRT)	(2 or 3) vs >3
Gender	Male vs female
Race	Caucasian vs Asian vs other
Region of the world (geographical)	Western Europe vs Eastern Europe vs North America vs Asia vs Other countries
Region of the world (regulatory)	Western countries vs Other countries
ECOG PS at baseline	0 or 1 vs 2
ISS staging at study entry	I vs II vs III
R-ISS staging at study entry	I vs II vs III
Cytogenetic abnormality (del(17p), t(4;14), t(14;16))	At least one vs. none
Cytogenetic abnormality del(17p)	Yes vs No
MM type at diagnosis	IgG vs non IgG
Baseline creatinine clearance (MDRD formula)	>60 ml/min vs ≤60 ml/min
Refractory to PI	Yes vs No
Refractory to lenalidomide	Yes vs No

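### The germline-marker Cox model has no race or region term, so the test of the marker's prognostic effect is open to ancestry confounding

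*SAP*

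**What the plan says.** SAP 2.4.8.1.2 sets the test for every immune genetic marker: "A cox regression model will be conducted separately for each genetic biomarker with a treatment effect, a biomarker effect and a biomarker×treatment interaction". No covariate or stratum is named. On genotype coding it says "For biomarkers coded as genotype (0, 1, 2), different coding may be investigated: additive, dominant or recessive", with no primary coding and no rule for choosing. On multiplicity it says "Benjamini-Hochberg multiple correction procedure will be used to control the False Discovery Rate", without a level or a definition of the family. It adds: "Additional analyses using ORR and OS instead of PFS might also be performed".

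The coding choice concerns FCGR2A and FCGR3A, for which SAP 2.1.8.1 says "the results will be of the form AA, Aa or aa". The KIR genes are binary: "The presence or absence of 16 KIR genes will be screened".

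Elsewhere the SAP collects race and geographical region at baseline (2.1.1). It lists both as covariates for PFS in Table 9, with race as "Caucasian vs Asian vs other". Appendix G shows enrolment across Western and Eastern Europe, North America, Asia (Japan, Korea, Taiwan) and other countries. The analysis is exploratory (1.2.3), and its results go to a separate report (2.1.8.1).

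**The concern.** Genotype is not randomized. Germline allele frequencies can differ by ancestry. If PFS also differs by ancestry or region, through disease biology or local care, the marker term picks up that difference even when the gene does nothing. The SAP evaluates confounding only for the treatment comparison (2.4.4.1.2), which randomization already protects. It makes no such provision for the marker comparison, which has no such protection.

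Benjamini-Hochberg assumes that each null p-value is valid. It corrects for the number of tests, not for bias within a test. A regional or ancestry difference could therefore be reported as a prognostic gene while the text says the false discovery rate is controlled.

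The open coding is a smaller, separate matter. If the smallest of three p-values for a gene were carried forward, it would not be uniform under the null.

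**Working it through.** **1. The plan's own figure.** SAP 1.3 gives 162 PFS events for HR 0.60, one-sided 2.5%, 90% power. Schoenfeld: 4 × (1.960 + 1.282)² / (ln 0.6)² = 161.1, rounded up to 162. It reproduces.

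**2. Information for the marker term.** With an interaction in the model, the marker term is the effect in the reference arm (taken here as Pd). At 15 patients a month, 1:1, expected events per arm by month t are 7.5 × [t − (1 − e^(−λt))/λ]. Here λ = ln 2/4 = 0.1733 for Pd and 0.6 × 0.1733 = 0.1040 for IPd. The arms total 162 at t = 17.6 months (the SAP says about 18), with about 91 events on Pd and 71 on IPd.

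**3. Size of the bias.** The documents give no ancestry shares, allele frequencies or ancestry effect on PFS, so these are assumed: share 15%, allele frequency 0.2 against 0.5, additive coding, null gene, two-sided 5%.

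- Mean allele count differs by 2 × (0.5 − 0.2) = 0.6.
- Between-group variance: 0.15 × 0.85 × 0.6² = 0.0459.
- Within-group variance: 0.85 × 2 × 0.2 × 0.8 + 0.15 × 2 × 0.5 × 0.5 = 0.347. Total 0.393.
- Regression of ancestry on allele count: 0.15 × 0.85 × 0.6 / 0.393 = 0.195.
- Bias in log HR per allele ≈ 0.195 × ln(ancestry HR).
- Standard error ≈ 1/√(91 × 0.393) = 0.167.
- Shift δ = bias/SE. Rejection rate = Φ(−1.96 + δ) + Φ(−1.96 − δ).

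| Ancestry HR | δ | Formula | Simulated, SAP model | Simulated, ancestry strata |
|---|---|---|---|---|
| 1.25 | 0.26 | 5.8% | 6.3% | 5.4% |
| 1.5 | 0.47 | 7.6% | 8.2% | 5.2% |
| 2.0 | 0.81 | 12.7% | 12.1% | 5.0% |

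The simulations used 300 patients, a cut at event 162 and 4,000 trials per row (Monte Carlo error 0.3 to 0.8 points).

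**4. Range over other assumptions** (simulated, additive coding).

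| Allele frequency | Share | Ancestry HR | SAP model | Ancestry strata |
|---|---|---|---|---|
| 0.2 vs 0.5 | 15% | 1.0 | 5.8% | 5.6% |
| 0.3 vs 0.4 | 15% | 1.5 | 4.8% | 4.5% |
| 0.2 vs 0.5 | 25% | 1.5 | 10.2% | 4.8% |
| 0.2 vs 0.5 | 25% | 2.0 | 20.0% | 5.5% |
| 0.1 vs 0.6 | 15% | 1.5 | 14.5% | 5.2% |
| 0.1 vs 0.6 | 15% | 2.0 | 29.6% | 5.6% |

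The unadjusted marker-by-treatment term stayed at 4.5% to 5.6% throughout. Ancestry was given the same effect in both arms in every run.

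**5. After Benjamini-Hochberg.** Assumptions: 22 null markers (2 genotype-coded, 20 binary), all with a frequency gap of 0.3; q = 5%; 15% share; treatment-stratified score tests of the marker. The chance of any false finding was 5.8% with no ancestry difference, 9.4% at ancestry HR 1.5 and 18.2% at HR 2.0. Adding ancestry strata gave 5.7% and 5.6% in the last two cases.

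**6. Coding alone, no ancestry effect.** Taking the best of three codings rejected 11.4% to 11.6% per gene, against 5.4% to 5.8% for additive. After Benjamini-Hochberg over the 22 markers, any false finding was 6.7% with the best coding against 5.8% with additive (6.7/5.8 = about 1.2 times), and 6.0% with every coding counted as a test. If the family were the two FCGR genes only, the best coding gave 12.1%. Ancestry strata do not cure this: best-of-three with strata still gave 10% to 12% per gene.

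**The case against.** The analysis is labelled univariate and exploratory, and no PFS, ORR or OS test depends on it. Listing race in Table 9 beside gender and renal function does not show that race affects PFS. The clear inflation needs an assumed ancestry hazard ratio of 1.5 or more together with a sizeable frequency gap. At the upper end, an ancestry HR of 2.0 is a larger effect than the one the trial was powered for (0.60, or 1/0.60 = 1.67 when inverted). All of this stands. It limits the consequence and makes the size conditional, but it does not make an unadjusted marker effect the better estimate.

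Timing also matters. SAP Table 10 schedules the biomarker analysis only at the primary PFS analysis, and SAP Table 1 shows that this analysis came before SAP version 3. The documents do not say whether the biomarker results already exist.

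A reader might infer more than the documents support:

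- That the SAP treats the coding as fixed. It says the opposite: "different coding may be investigated: additive, dominant or recessive". Nor does it say that the best p-value is kept.
- That null genes are declared at twice the nominal rate. Doubling is a per-gene figure before Benjamini-Hochberg. It requires best-of-three selection or strong ancestry assumptions.
- That the coding issue covers all markers. The KIR genes have no coding choice.
- That the predictive test is confounded as well. Ancestry acting equally in both arms does not inflate the interaction.
- That the IRT strata are needed. No link between germline genotype and age or prior lines has been shown.

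**Conclusion.** The concern holds in conditional form. The marker main effect is tested without adjustment for race or region in a multi-ancestry trial, and neither randomization nor Benjamini-Hochberg protects it. In the central illustration the per-gene false-positive rate is about 6% to 13% against a nominal 5%. It is nil when allele frequencies are similar or ancestry has little effect on PFS, and higher under stronger assumptions. The direction of the problem follows from the model; its size rests on inputs that the documents do not give. Stratifying by ancestry restored 4.5% to 5.6% in every scenario with one fixed coding.

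The coding and the Benjamini-Hochberg family are mainly missing detail, confined to FCGR2A and FCGR3A, and worth about 1.2 times after correction over 22 assumed markers. Adjustment is a cheap improvement to an exploratory analysis. The primary and key secondary conclusions are untouched.

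**What to change.** In SAP 2.4.8.1.2:

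1. Adjust the Cox model for race, or stratify by it, using the Table 9 grouping or one combined race/region grouping. Apply the same adjustment to any ORR or OS version. Keep the unadjusted model as a sensitivity analysis.
2. Keep the grouping coarse. Crossing three race groups with five regions and the 2 × 2 IRT strata gives 3 × 5 × 4 = 60 cells for 162 events, under 3 per cell.
3. For FCGR2A and FCGR3A, let one named coding (for example additive) enter Benjamini-Hochberg, or enter every coding tried as a separate test. State the false discovery level and which tests form the family.
4. If biomarker results have already been produced, report the adjusted model and the coding choice as added afterwards.

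No new data are needed. The cost is precision for ancestry-linked markers. The standard error grows by at most about 1/√(1 − R²), where R² is the share of marker variance explained by ancestry. In the central case R² = 0.0459/0.393 = 0.117, a factor of 1.06. For frequencies 0.1 against 0.6, R² = 0.1275/(0.1275 + 0.225) = 0.362, a factor of 1.25. So intervals are slightly wider for most markers, and noticeably wider only where genotype largely tracks ancestry.

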#### **2.4.9 Analyses of quality of life/health economics variables**

PRO endpoints for each of the 3 selected PRO/HRQL and health utility instruments (EORTC QLQ-C30, QLQ-MY20 and EQ-5D-5L) will be analyzed in patients from the safety population who have completed the baseline and at least 1 post baseline assessment.

For each questionnaire the compliance profile over time will be summarized on the safety population (number and percentage of forms received versus expected, and number and percentage of forms evaluable versus expected). Reasons for non-completion will be summarized on the safety population.

Descriptive statistics of the mean change scores by treatment arms (from baseline to each cycle, from baseline to EOT and from baseline to 60 days after last study treatment) will be conducted for each PRO as follows:

- QLQ-C30: global health status/QoL summary score, the five functional subscale scores (physical, emotional, cognitive, role and social), the three symptom subscale scores (fatigue, nausea/vomiting and pain) and the six additional single item scores (dyspnea, insomnia, appetite loss, constipation, diarrhea, and financial difficulties);
- MY20: future perspective, body image, disease symptoms and side effects of treatment subscale scores;
- EQ-5D-5L: health state utility value and VAS scores.

Additional analyses (eg responder analyses for each PRO summary, subscale and symptom score and EQ-5D shift tables) could be presented in a separate document.

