Amended Clinical Trial Protocol 01 (GB)	United Kingdom	24-Feb-2017, version 1 (electronic 1.0)
Amended Clinical Trial Protocol 01	All	01-Nov-2016, version 1 (electronic 1.0)
Protocol Amendment 01	All	01-Nov-2016, version 1 (electronic 1.0)
Clinical Trial Protocol	All	04-Aug-2016, version 1 (electronic 2.0)

AMENDED PROTOCOL 07 (26-Nov-2020)

This amended protocol (amendment 07) is considered to be substantial based on the criteria set forth in Article 10(a) of Directive 2001/20/EC of the European Parliament and the Council of the European Union.

OVERALL RATIONALE FOR THE AMENDMENT

A risk of hepatitis reactivation has been identified in the SAR650984 Investigator's Brochure edition 11 (30-Apr-2020).

Protocol amendment summary of changes table

Section # and Name	Description of Change	Brief Rationale
1.2 Study Flow chart; 8.2.5 Other toxicities	Additional hepatitis viral serology if HBV status unknown before treatment start, to be repeated if clinically indicated.	A risk of hepatitis reactivation has been identified.
8.2.5 Other toxicities; 10.1.6 Post PFS study cut-off date; 10.1.7 Post final OS study cut-off date	Description of study treatment discontinuation and restart procedure in case of viral reactivation.	A risk of hepatitis reactivation has been identified.

Section # and Name	Description of Change	Brief Rationale
8.2.5 Other toxicities; 10.1.6 Post PFS study cut-off date; 10.1.7 Post final OS study cut-off date	Description of monitoring of alanine aminotransferase (ALT) and aspartate aminotransferase (AST) in case of viral reactivation.	A risk of hepatitis reactivation has been identified.
8.2.1 Study treatments (IMP); 8.2.4 Infusion reactions	Infusion rate of isatuximab has been revised.	In line with the currently approved infusion rate for the combination isatuximab, pomalidomide and dexamethasone.
8.1.1.1 Pharmaceutical form; 8.1.1.2 Dilution method	Dextrose 5% can also be used for isatuximab dilution.	Clarification
Clinical Trial Summary; 1.3 Pharmacokinetic/ Pharmacodynamic Flow Chart; 10.1.7 Post final OS study cut-off date	Removal of anti-drug antibodies tests after final analysis cut-off date leading to shortening of follow-up period to 30 days after last study treatment use for patients still on treatment at the time of amended protocol 07.	ADA sampling obtained from all isatuximab studies have provided enough relevant information in terms of immunogenicity profile.

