9.3.3 Patient-reported outcomes (HRQL/health economic variables/other endpoints)

Patient-reported outcome measures to be included are the European Organisation for Research and Treatment of Cancer (EORTC) Quality of Life questionnaire with 30 questions (QLQ-C30), the EORTC Myeloma Module with 20 items (QLQ-MY20), and the European Quality of Life Group measure with 5 dimensions and 5 levels per dimension (EQ-5D-5L). Each questionnaire is described in this section.

Timing of Assessments

All three questionnaires have been designed for self-completion.

Cycle 1 Day 1 (prior to study treatment administration) will serve as the baseline assessment for all patients. All the electronic patient-reported outcomes (ePROs) are to be completed by the patient using the tablet provided via the study, before other clinician assessments are conducted, and before his/her clinical condition, treatment plan, AEs, etc are discussed. The latter is to ensure the objectivity of the patient responses free from their emotional reactions to prevent bias. The patient is to complete ePRO questionnaires on his or her own.

There will be a minimum of 20 minutes time allocated to train patients on ePRO technology at Cycle 1 Day 1 visit. Training assistance will be provided for subsequent cycles, EOT, and follow-up if the patient requests a refresher.

While on treatment, ePROs are to be administered prior to treatment on Day 1 of every cycle, at the EOT visit and at 60 (± 5 days) days after last study treatment administration. The time estimated to complete the EORTC QLQ-C30 and the EORTC QLQ-MY20 is approximately 10-15 minutes. The time estimated to complete the EQ-5D-5L is approximately 5 to 10 minutes.

In order to optimize compliance of the patient, and to ensure the completeness of the ePRO data, it is recommended that a key person (eg, research nurse) is assigned and responsible at each center for ePRO data collection.

A statistical analysis plan for the three ePROs will be detailed in the SAP.

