11 STATISTICAL CONSIDERATIONS

The statistical considerations presented in this section forms the basis for the Statistical Analysis Plan (SAP), which will provide accurate definitions and detailed specifications for the analyses to be performed on the data collected from this study. A final SAP will be issued prior to first patient treated.

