11.4.6 Analyses of patient reported outcomes (HRQL/health economics) variables

Change from baseline for the following variables from EORTC QLQ-C30: global HRQL, five functional scales (physical, emotional, cognitive, role and social) and nine symptom domains (fatigue, nausea/vomiting, pain, dyspnea, insomnia, appetite loss, constipation, diarrhea, and financial difficulties); for the MY-20: future perspective, body image, disease symptoms and side effects of treatment; and for the EQ-5D-5L: health state utility value and VAS scores will be analyzed with an MMRM approach. Descriptive statistics including number of patients, mean and standard error will be provided. In addition, LS means, difference in LS means, the corresponding 95% CI's and the p-values will be provided for comparison between treatment arms.

Responder analyses will also be conducted using established MIDs (to be described in SAP) for each of the above variables.

Each of the following criteria will be assessed via a comparison of change scores from baseline to EOT and 60 days after last study treatment administration between treatment arms:

- A) Disease-specific HRQL (EORTC QLQ-C30)

- B) Disease- and treatment-related symptoms (EORTC QLQ-C30 and MY20)
- C) Health state utility (EQ-5D-5L)
- D) Health status (EQ-5D-5L visual analogue scale).

In addition, responder analyses will be conducted:

1. For those who improve.
2. For those who deteriorate.
3. For those who stay the same.
4. Time to definitive improvement, and time to definitive deterioration will be based using the CIDs defined in [Appendix H](#), [Appendix I](#), and [Appendix J](#).
5. Deterioration will be considered definitive if no later improvement above the defined thresholds (CIDs defined in [Appendix H](#), [Appendix I](#), and [Appendix J](#)) are observed, prior to further anticancer therapy.
6. Improvement will be considered definitive if no later deterioration above the defined thresholds (CIDs defined in [Appendix H](#), [Appendix I](#), and [Appendix J](#)) are observed, prior to further anticancer therapy.

Full details will be provided in the SAP.

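### Protocol 11.4.6 commits to an MMRM between-arm comparison of HRQL; SAP 2.4.9 specifies only descriptive means by arm and does not state or explain the difference

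*SAP*

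**What the plan says.** **Protocol 11.4.6.** The list of change-from-baseline scores ends with the instruction that "health state utility value and VAS scores will be analyzed with an MMRM approach". The output is fixed too: "In addition, LS means, difference in LS means, the corresponding 95% CI's and the p-values will be provided for comparison between treatment arms". Disease-specific HRQL, symptoms, utility and health status are each to be "assessed via a comparison of change scores from baseline to EOT and 60 days after last study treatment administration between treatment arms". On thresholds: "Responder analyses will also be conducted using established MIDs (to be described in SAP) for each of the above variables". The section also lists time to definitive improvement and to definitive deterioration, and leaves full details to the SAP. Protocol 11 describes the SAP as the document "which will provide accurate definitions and detailed specifications for the analyses to be performed on the data collected from this study".

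**SAP 2.4.9.** For the same three questionnaires it specifies compliance tables, reasons for non-completion, and "Descriptive statistics of the mean change scores by treatment arms (from baseline to each cycle, from baseline to EOT and from baseline to 60 days", the 60 days running from the final dose. Responder analyses and EQ-5D shift tables are examples of additional work that may appear in a separate document. No longitudinal model, between-arm difference, confidence interval or p-value is named.

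**Change records.** SAP 1.5 lists two changes made between the protocol and SAP version 1; the one on PROs concerns the analysis population. SAP Table 1 lists the ePRO analyses among those updated in version 2 (07-Nov-2018), under a rationale of clarification, without saying what was updated.

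**The concern.** The protocol assigns the detail to the SAP, and the SAP omits the analysis it was meant to detail. A programmer following the SAP would produce no adjusted treatment difference for HRQL, although HRQL is a stated secondary objective and the protocol promises a comparison.

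The choice of method matters because of who contributes data. Protocol 9.3.3 says "While on treatment, ePROs are to be administered prior to treatment on Day 1 of every cycle", so by-cycle means describe patients still on treatment, and that share may differ by arm. The compliance tables would disclose this, but simple means by arm take no account of it. An MMRM uses each patient's earlier scores and yields a between-arm estimate with its uncertainty.

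**Working it through.** The check is mainly a comparison of texts.

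**1. Scores covered by the protocol's MMRM.** QLQ-C30: 1 global + 5 functional + 9 symptom = 15. MY20: 4. EQ-5D-5L: 2. Total 15 + 4 + 2 = 21. SAP 2.4.9 lists the same scores (1 + 5 + 3 + 6 + 4 + 2 = 21), so the outcomes agree and the analyses differ.

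**2. Promise against specification.**

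| Item | Protocol 11.4.6 | SAP 2.4.9 |
|---|---|---|
| Model for change | MMRM | none |
| Between-arm estimate | LS-mean difference, 95% CI, p-value | none |
| Change to EOT and Day 60 | compared between arms | described by arm |
| Responder analyses | committed | optional, separate document |
| Time to definitive change | committed | not mentioned |

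SAP 2.4 defines descriptive statistics for continuous data as n, mean, SD, median, minimum and maximum by group; SAP 2.5.3 bases them on observed data. The only mixed-effect model in the SAP is for population PK (2.4.6).

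**3. Is the difference recorded?** SAP 1.5 covers changes up to version 1 only, so it cannot show whether a later change was logged. The version 2 entry may or may not be the record of this change; it gives no content. The version 3 entries do not mention PROs.

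**4. Are the current documents aligned?** SAP version 3 is dated 20-Oct-2020 and protocol Amendment 07 is dated 26-Nov-2020. The later document still contains the MMRM text.

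**5. Illustration of retention.** Assume exponential PFS with PFS standing in for time on treatment. Planned medians are 4 months (Pd) and 6.67 months (IPd), from Protocol 11.1. Cycle c starts at t = (c − 1) × 28/30.44 months. The share still on treatment is 0.5^(t/4) for Pd and 0.5^(t/6.67) for IPd.

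| Cycle | t (months) | Pd | IPd | IPd:Pd |
|---|---|---|---|---|
| 3 | 1.84 | 0.727 | 0.826 | 1.14 |
| 5 | 3.68 | 0.529 | 0.682 | 1.29 |
| 7 | 5.52 | 0.384 | 0.564 | 1.47 |

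If PFS is equal in the two arms, the ratio is 1.00 at every cycle. The range at cycle 7 is therefore 1.00 to 1.47 between no effect and the planned hazard ratio of 0.60.

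**The case against.** Several points can fairly be made for the plan.

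- **The change may have been logged.** A reader might infer that the MMRM was dropped without any record. The documents do not support that: SAP 1.5 stops at version 1, version 1 is not available, and the version 2 entry on ePRO analyses could be the record. What stands is that no entry says what changed or why.
- **The protocol text may simply be carried over.** The listed changes in Amendment 07 concern other matters, and its only listed statistical section is 11.4.7. Its date shows that the documents are not aligned; it is not a fresh commitment to the MMRM.
- **The objective is only to assess HRQL, and secondary endpoints are descriptive.** The comparison does come from Protocol 11.4.6 and the protocol summary, not from the objective's wording. But the descriptive-only sentence closes the section on other secondary efficacy endpoints (Protocol 11.4.2.2.2), whereas PROs have their own section promising estimates, CIs and p-values. SAP 2.4.4.3 gives even the exploratory PFS2 a hazard ratio, CI and descriptive p-value.
- **An MMRM also uses observed data.** This stands. It accounts for drop-out only under missing-at-random, which is doubtful when forms stop around progression. The EOT and Day 60 summaries are also not limited to patients still on treatment.
- **A difference can be derived from n, mean and SD.** It can, but it would be unadjusted and is not the comparison promised.
- **The MMRM may have been run.** SAP 2.4.9 allows a separate document, so its absence from the results cannot be assumed.

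**Conclusion.** The inconsistency is real. The protocol specifies model-based between-arm estimates for 21 scores; the SAP specifies none, makes responder analyses optional, and does not state or explain the departure. When the MMRM was left out cannot be established from these documents.

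The consequence is limited. HRQL is outside the PFS-ORR-OS testing order, so nothing confirmatory changes. What is lost is the planned adjusted estimate for a secondary objective.

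The retention figures might be read as the size of a bias in HRQL. They are not: they rest on PFS as a proxy for time on treatment, although treatment also stops for adverse events or patient wish and continues until progression is confirmed. They show only that the arms may contribute different fractions of patients to the by-cycle means. Nor should the MMRM be read as a complete cure for that attrition.

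**What to change.** - **Restore the MMRM in SAP 2.4.9.** The protocol names no model terms, so state them: for example treatment, visit, treatment-by-visit and baseline score, with the covariance structure. State the missing-at-random assumption and note that it may not hold around progression.
- **Report it descriptively.** Give LS-mean differences with 95% CIs and descriptive p-values, outside the alpha hierarchy. Label the model details as specified after the primary PFS analysis, since SAP version 3 already postdates it.
- **Settle the other promises.** For the EOT and Day 60 comparisons and the responder and time-to-definitive analyses, either deliver them or record and justify the departure in SAP Table 1 and align Protocol 11.4.6.
- **Complete the log.** Say what the version 2 update of the ePRO analyses changed.
- **Results.** SAP Table 10 schedules HRQL only at the primary PFS analysis. If no MMRM was reported then or in a separate document, add it as an addendum to the HRQL results.

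The cost is SAP wording, a fuller log entry and one standard mixed-model program on data already collected. Declaring the MMRM departure and amending Protocol 11.4.6 would remove the contradiction at less cost, but would leave no adjusted estimate.
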